## 10. ASSESSMENT OF SAFETY

The Principal Investigator is responsible for ensuring that all staff involved in the study is

familiar with the content of this section.

## **10.1. Safety parameters**

### **10.1.1. Definition of adverse events**

An adverse event is the development of an undesirable medical condition (other than progression of the malignancy under evaluation) or the deterioration of a pre-existing medical condition following or during exposure to a pharmaceutical product, whether or not considered causally related to the product. An undesirable medical condition can be symptoms (e.g., nausea, chest pain), signs (e.g., tachycardia, enlarged liver) or the abnormal results of an investigation (e.g., laboratory findings, electrocardiogram). In clinical studies, an AE can include an undesirable medical condition occurring at any time, including run-in or washout periods, even if no study treatment has been administered.

The term AE is used to include both serious and non-serious AEs.

### **10.1.2. Definition of serious adverse events**

A serious adverse event is an AE occurring during any study phase (i.e., screening, run-in, treatment, wash-out, follow-up), at any dose of the study drugs that fulfils one or more of the following criteria:

- Results in death
- Is immediately life-threatening
- Requires in-patient hospitalization or prolongation of existing hospitalization
- Results in persistent or significant disability or incapacity
- Is a congenital abnormality or birth defect in offspring of the patient
- Is an important medical event that may jeopardize the patient or may require medical intervention to prevent one of the outcomes listed above.

The causality of SAEs (their relationship to all study treatment/procedures) will be assessed by the investigator(s) and communicated to the sponsor.

### **10.1.3. Durvalumab + tremelimumab adverse events of special interest**

An adverse event of special interest (AESI) is one of scientific and medical interest specific to understanding of the Investigational Product and may require close monitoring and rapid communication by the investigator to the sponsor. An AESI may be serious or non-serious. The rapid reporting of AESIs allows ongoing surveillance of these events in order to characterize and understand them in association with the use of this investigational product.

AESIs for durvalumab ± tremelimumab include but are not limited to events with a

potential inflammatory or immune-mediated mechanism and which may require more frequent monitoring and/or interventions such as steroids, immunosuppressants and/or hormone replacement therapy. These AESIs are being closely monitored in clinical studies with durvalumab monotherapy and combination therapy. An immune-mediated adverse event (imAE) is defined as an AESI that is associated with drug exposure and is consistent with an immune-mediated mechanism of action and where there is no clear alternate etiology. Serologic, immunologic, and histologic (biopsy) data, as appropriate, should be used to support an imAE diagnosis. Appropriate efforts should be made to rule out neoplastic, infectious, metabolic, toxin, or other etiologic causes of the imAE.

If the Investigator has any questions in regards to an event being an imAE, the Investigator should promptly contact the Study Physician.

AESIs observed with durvalumab  $\pm$  tremelimumab include:

- Diarrhea / Colitis
- Intestinal perforation
- Pneumonitis / ILD
- ALT/AST increases / hepatitis / hepatotoxicity
- Neuropathy / neuromuscular toxicity (e.g. Guillain-Barré, and myasthenia gravis)
- Myositis/polymyositis
- Endocrinopathies (i.e. events of hypophysitis, hypopituitarism, adrenal insufficiency, diabetes insipidus, hyper- and hypothyroidism and type I diabetes mellitus)
- Rash / Dermatitis
- Nephritis / Blood creatinine increases
- Pancreatitis (or labs suggestive of pancreatitis - increased serum lipase , increased serum amylase).
- Myocarditis
- Other inflammatory responses that are rare with a potential immune-mediated aetiology are also considered as AESIs and include, but are not limited to, pericarditis, sarcoidosis, uveitis and other events involving the eye, skin, haematological, rheumatological events, vasculitis, non-infectious meningitis and non-infectious encephalitis. It is possible that events with an inflammatory or immune mediated mechanism could occur in nearly all organs.

In addition, infusion-related reactions and hypersensitivity/anaphylactic reactions with a different underlying pharmacological etiology are also considered AESIs.

Further information on these risks (e.g. presenting symptoms) can be found in the current version of the durvalumab and tremelimumab Investigator's Brochures. More specific guidelines for their evaluation and treatment are described in detail in the Dosing Modification and Toxicity Management Guidelines (see Appendix 1). These guidelines

have been prepared by the Sponsor to assist the Investigator in the exercise of his/her clinical judgment in treating these types of toxicities. These guidelines apply to AEs considered causally related to the study drug/study regimen by the reporting investigator.

If new or worsening pulmonary symptoms (e.g. dyspnea) or radiological abnormality suggestive of pneumonitis/interstitial lung disease is observed, toxicity management as described in detail in the Dosing Modification and Toxicity Management Guidelines (see Appendix 1) will be applied. The results of the full diagnostic workup (including high-resolution computed tomography (HRCT), blood and sputum culture, hematological parameters etc) will be captured in the eCRF. It is strongly recommended to perform a full diagnostic workup, to exclude alternative causes such as lymphangitic carcinomatosis, infection, allergy, cardiogenic edema, or pulmonary hemorrhage. In the presence of confirmatory HRCT scans where other causes of respiratory symptoms have been excluded, a diagnosis of pneumonitis (ILD) should be considered and the Dosing Modification and Toxicity Management Guidelines should be followed.

### **Pneumonitis (ILD) investigation**

The following assessments, and additional assessments if required, will be performed to enhance the investigation and diagnosis of potential cases of pneumonitis. The results of the assessment will be collected.

- Physical examination
- Signs and symptoms (cough, shortness of breath and pyrexia, etc.) including auscultation for lung field will be assessed.
- Saturation of peripheral oxygen (SpO2)
- Other items
- When pneumonitis (ILD) is suspected during study treatment, the following markers should be measured where possible:
  1. ILD Markers (KL-6, SP-D) and β-D-glucan
  2. Tumour markers: Particular tumour markers which are related to disease progression.
  3. Additional Clinical chemistry: CRP, LDH

## **10.2. Assessment of safety parameters**

### **10.2.1. Assessment of severity**

Assessment of severity is one of the responsibilities of the investigator in the evaluation of AEs and SAEs. Severity will be graded according to the NCI CTCAE v4.03.

The determination of severity for all other events not listed in the CTCAE should be

made by the investigator based upon medical judgment and the severity categories of Grade 1 to 5 as defined below.

- Grade 1 (mild) An event that is usually transient and may require only minimal treatment or therapeutic intervention. The event does not generally interfere with usual activities of daily living.
- Grade 2 (moderate) An event that is usually alleviated with additional specific therapeutic intervention. The event interferes with usual activities of daily living, causing discomfort but poses no significant or permanent risk of harm to the patient.
- Grade 3 (severe) An event that requires intensive therapeutic intervention. The event interrupts usual activities of daily living, or significantly affects the clinical status of the patient.
- Grade 4 (life threatening) An event, and/or its immediate sequelae, that is associated with an imminent risk of death or with physical or mental disabilities that affect or limit the ability of the patient to perform activities of daily living (eating, ambulation, toileting, etc).
- Grade 5 (fatal) Death (loss of life) as a result of an event.

It is important to distinguish between serious criteria and severity of an AE. Severity is a measure of intensity whereas seriousness is defined by the criteria in Section 10.2.1. A Grade 3 AE need not necessarily be considered an SAE. For example, a Grade 3 headache that persists for several hours may not meet the regulatory definition of an SAE and would be considered a non serious event, whereas a Grade 2 seizure resulting in a hospital admission would be considered an SAE.

### **10.2.2. Assessment of relationship**

The Investigator's assessment of causality must be provided for all AEs (serious and non-serious); the Investigator must record the causal relationship in the eCRF, as appropriate, and report such an assessment in accordance with the serious adverse reporting requirements if applicable. An Investigator's causality assessment is the determination of whether there exists a reasonable possibility that the study treatment caused or contributed to an AE; generally, the facts (evidence) or arguments to suggest a causal relationship should be provided.

If the Investigator does not know whether or not the study treatment caused the event, then the event will be handled as "related to study treatment" for reporting purposes.

If the Investigator's causality assessment is "unknown but not related to study treatment", this should be clearly documented on study records.

In addition, if the Investigator determines an SAE is associated with study procedures,

the Investigator must record this causal relationship in the source documents and eCRF, as appropriate, and report such an assessment in accordance with the SAE reporting requirements, if applicable.

### **10.3. Recording of adverse events and serious adverse events**

Adverse events will be recorded eCRF using a recognized medical term or diagnosis that accurately reflects the event. Adverse events will be assessed by the investigator for severity, relationship to the investigational product, possible etiologies, and whether the event meets criteria of an SAE and therefore requires immediate notification to the sponsor.

The following variables will be collected for each AE:

In addition, the following variables will be collected for SAEs as applicable:

- AE (verbatim)
- The date when the AE started and stopped
- The maximum CTCAE grade reported
- Changes in CTCAE grade
- Whether the AE is serious or not
- Investigator causality rating against the IPs (yes or no)
- Action taken with regard to IPs
- Administration of treatment for the AE
- Outcome

In addition, the following variables will be collected for SAEs:

- Date the AE met criteria for SAE
- Date the Investigator became aware of the SAE
- Seriousness criteria fulfilled
- Date of hospitalization
- Date of discharge
- Probable cause of death
- Date of death
- Whether an autopsy was performed
- Causality assessment in relation to study procedure(s)
- Causality assessment in relation to other medication, as explained in Section 10.2.2
- Description of the SAE

The grading scales found in the revised NCI CTCAE version 4.03 will be utilized for all events with an assigned CTCAE grading. For those events without assigned CTCAE

grades, the recommendation in the CTCAE criteria that converts mild, moderate, and severe events into CTCAE grades should be used. A copy of the CTCAE version 4.03 can be downloaded from the Cancer Therapy Evaluation Program website (<http://ctep.cancer.gov>).

Events, which are unequivocally due to disease progression, should not be reported as an AE during the study.

#### **10.3.1. Study recording period and follow-up for adverse events and serious adverse events**

Adverse events and serious adverse events will be recorded from time of signature of informed consent, throughout the treatment period and including the follow-up period (90 days after the last dose of durvalumab + tremelimumab).

During the study, all AEs and SAEs should be proactively followed up for each patient. Every effort should be made to obtain a resolution for all events, even if the events continue after discontinuation/study completion.

If a patient discontinues from treatment for reasons other than disease progression, and therefore continues to have tumor assessments, drug or procedure-related SAEs must be captured until the patient is considered to have confirmed PD and will have no further tumor assessments.

The investigator is responsible for following all SAEs until resolution, until the patient returns to baseline status, or until the condition has stabilized with the expectation that it will remain chronic, even if this extends beyond study participation.

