## **3. STUDY DESIGN**

### **3.1. Overview of study design**

This is an open-label, multicenter, phase II trial of the combination of durvalumab plus tremelimumab with concurrent normofractionated radiotherapy in patients with localized muscle invasive bladder cancer treated with a selective multimodality bladder conservative approach. The study will be conducted in a small group of centers with multidisciplinary teams with wide experience in multimodality bladder preservation therapy (7 centers belonging to SOGUG).

The treatment consisted of initial transurethral resection (TUR) of the tumor, with multiple random biopsies of normal-appearing bladder urothelium, followed by durvalumab 1500 mg i.v. plus tremelimumab 75 mg i.v., every 4 weeks for a total of 3

doses. Two weeks after the initiation of immunotherapy, normofractionated external-beam radiotherapy with high-energy photons will be started. Radiotherapy will be administered concurrently with immunotherapy at doses of 46 Gy to the minor pelvis and 64-66 Gy to the bladder. Six weeks after the end of radiotherapy as an efficacy determination, ALL patients will undergo a new cystoscopy with biopsies of the tumor bed and all residual present lesions. Response is defined as an absence of invasive cancer at post immunotherapy biopsy ( $\leq$ cT1). Patients with response to immunotherapy will be candidates to bladder preservation, whereas in those with residual muscle invasive tumor the possibility of salvage radical cystectomy must be evaluated. Patients developing an isolated bladder invasive relapse during follow-up will be also possible candidates to salvage cystectomy, whereas those developing a superficial relapse in the preserved bladder will be managed with TUR and intravesical BCG.

To monitor accurately the potential toxicity of radiotherapy associated with durvalumab and tremelimumab, an initial cohort of 5 patients of first Simon Optimax stage of 12 patients, will be treated. If no dose limiting toxicity is observed in  $\geq$ 2 of these patients in the 12 weeks of observation period, the rest of patients will be treated at full doses. In contrast, if severe toxicity is observed in  $\geq$ 2 of these patients, 3 additional patients will be treated. If dose limiting toxicity is seen in one of these additional patients, the therapeutic regimen will be modified in the subsequent ones, administering full doses of durvalumab but discontinuing tremelimumab after the first dose.

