### **8.1.4. Safety**

Safety follow-up visits will be scheduled up to 90 days after the last dose of study treatment, the procedures to be performed are the same that for EOT visit except for peripheral blood collection and CT scan that should not been performed in this visit, unless PI criteria as per normal practice

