#### **10.3.9. Reporting of serious adverse events**

All SAEs will be reported, whether or not considered causally related to the investigational product, or to the study procedure(s). The reporting period for SAEs is the period immediately following the time that written informed consent is obtained through 90 days after the last dose of durvalumab or until the initiation of alternative anticancer therapy. The investigator and/or Sponsor are responsible for informing the Regulatory Authority of the SAE as per local requirements.

Each AE is to be assessed to determine if it meets the criteria for SAEs. If an SAE occurs, expedited reporting will follow local and international regulations, as appropriate.

The sponsor must inform the AEMPS of any Suspected serious or unexpected serious adverse events (SUSAR) that occur in accordance with the reporting obligations, and will concurrently forward all such reports to AstraZeneca. A copy of the report must be sent by e-mail to AstraZeneca at the time the event is reported to the AEMPS by the sponsor.

\* A cover page should accompany the SAE form indicating the following:

- External Scientific Research (ESR)
- The investigator's name and address
- The trial name/title and AstraZeneca ESR reference number

\* Send SAE report and accompanying cover page by way of Email to

If a non-serious AE becomes serious, the same process described before will be followed.

Serious adverse events that do not require expedited reporting to the AEMPS need to be reported to AstraZeneca preferably using the MedDRA coding language for serious adverse events. This information should be reported on a monthly basis and under no circumstance less frequently than quarterly.

The following reportable events must be submitted to the sponsor within 24 hours (or immediately for death or life-threatening events).

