## 2. SAFETY ANALYSIS

### 2.1. SAFETY SUMMARY: ALL EVENTS IN OVERALL (SAFETY POPULATION)

Table 198: Safety

	N	%	LL IC 95%	UL IC 95%
SAE	No			
	Yes			
	Total			
SAE related	No			
	Yes			
	Total			
AE relationship to treatment (any treatment)	No			
	Yes			
	Total			
AE Grade $\geq$ 3 related to any treatment	No			
	Yes			
	Total			
AE related to both treatments (Durva-Treme)	No			
	Yes			
	Total			
AE related to all treatments (Durva-Treme-Radiotherapy)	No			
	Yes			
	Total			
Adverse Events Related Durvalumab	No			
	Yes			
	Total			
Adverse Events Related RT	No			
	Yes			
	Total			
Adverse Events Related Tremelimumab	No			
	Yes			
	Total			
AE	Yes			
	Total			
AE Grade $\geq$ 3	No			
	Yes			
	Total			

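### Section 10.3.1 extends related-SAE capture to progression only for patients who stop treatment early, and SAP Table 198 sets no onset window for the rows that count these events

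*Combined protocol and SAP*

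**What the plan says.** Section 10.3.1 records AEs and SAEs from consent "throughout the treatment period and including the follow-up period (90 days after the last dose of durvalumab + tremelimumab"). It then adds a rule for one group: "If a patient discontinues from treatment for reasons other than disease progression, and therefore continues to have tumor assessments", then "drug or procedure-related SAEs must be captured until the patient is considered to have confirmed PD and will have no further tumor assessments". A patient who completes treatment is not named in that rule.

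Other places set the end of safety capture differently:

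- Section 8.1.4: "Safety follow-up visits will be scheduled up to 90 days after the last dose of study treatment".
- Section 8.1.5: 90 days after the last durvalumab and tremelimumab administration.
- Section 10.3.9, for SAE reporting: "through 90 days after the last dose of durvalumab or until the initiation of alternative anticancer therapy". It has no extension for early stoppers.
- Section 10.3.9.1: deaths within 90 days of the last combination dose. After that, a death from an event judged to be late-onset drug toxicity is still reported as an SAE, in any patient.
- Section 11.2.1: safety analysis weekly on treatment, then every three months for late radiotherapy toxicity.
- The schedules in the synopsis and in section 3.2: AE/SAE assessment is marked in the Follow-up column for every patient, with no end date.

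SAP Table 198 gives N, percentage and 95% limits for rows such as SAE, SAE related and "AE relationship to treatment (any treatment"). It states no onset window, no patient-time and no split by capture rule. Protocol Table 8 plans frequency tables only.

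**The concern.** The length of the related-SAE record depends on how treatment ended. The reason given in section 10.3.1 is that the patient goes on having tumour assessments. That is equally true of completers, who are imaged on the same follow-up schedule (sections 3.1 and 6).

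Early stopping for toxicity is foreseen: SAP Table 39 lists unacceptable toxicity as an end-of-treatment reason. Length of capture is therefore tied to the kind of outcome being counted. A crude proportion of patients with a related SAE then reflects partly the risk and partly how many patients stopped early, and it describes no single risk period. The differing anchors add to this, because one site could stop recording a completer at day 147 while another continues through follow-up.

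**Working it through.** The plan states no design figure on this point, so the check rebuilds the calendar from the protocol's timings and compares capture periods.

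**Inputs.** Three doses every 4 weeks (section 6), so days 1, 29 and 57. Radiotherapy from two weeks after the first dose (section 6), so day 15; 32 fractions, 5 per week (section 1.3.3). Recording for 90 days after the last immunotherapy dose (section 10.3.1). Closure 2 years after the last inclusion (section 3.1). First patient 24 January 2019 and last patient in 3Q 2020 (section 13.4). All 32 patients received at least 2 durvalumab doses (SAP section 3.1).

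**Calendar check.** With fractions on weekdays and a Monday start, fraction 32 falls on day 15 + 6 × 7 + 1 = 58, which is 57 days after the first dose. Twelve weeks is 84 days, and (84 − 57)/7 = 3.9 weeks. This agrees with the synopsis, which equates 12 weeks with 4 weeks after radiotherapy.

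**General AE window (last dose + 90 days).**

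- Two doses: 29 + 90 = day 119, or 118 days from first dose.
- Three doses: 57 + 90 = day 147, or 146 days from first dose.
- Difference 28 days; ratio 146/118 = 1.24, before any dose delays.

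**Related-SAE period under section 10.3.1, if progression never occurs.**

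- Completer: 146 days from first dose.
- Early stopper, last patient enrolled: 2 years, about 730 days; 730/146 = 5.0.
- Early stopper, first patient, counting from 24 January 2019: closure between 1 July and 30 September 2022 gives 1254 to 1345 days; 1254/146 = 8.6 and 1345/146 = 9.2.

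Confirmed progression shortens the early stopper's period.

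**Illustration of the effect on the pooled percentage.** The documents give no late-event rate, so these values are assumptions: a constant hazard h of 0.05 to 0.20 first related SAEs per patient-year from day 146 to 2 years, no progression, and k = 3 to 10 early stoppers among 32. The extra time is 2 − 146/365.25 = 1.60 years, and the probability of an event in it is p = 1 − exp(−1.60h).

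- h = 0.05: p = 7.7%. h = 0.10: p = 14.8%. h = 0.20: p = 27.4%.
- Capture in early stoppers only adds k × p/32. Lowest: 3 × 7.7/32 = 0.7 points. Highest: 10 × 27.4/32 = 8.6 points.
- Capture in all 32 would add p itself, 7.7 to 27.4 points.

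Under these assumptions the reported figure lies between the proportion within the common window and the two-year proportion. Where it lies is set by k.

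**The case against.** The strongest reply is that other parts of the protocol look after completers too. Both schedules mark AE/SAE assessment at follow-up for everyone, section 11.2.1 plans three-monthly late toxicity, and section 10.3.9.1 covers late fatal toxicity. A reader might infer from section 10.3.1 that completers go unobserved after day 147; the documents do not support that. What stands is a difference in the stated recording duty and a conflict between passages, because none of these provisions amends sections 10.3.1 or 10.3.9.

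Other stronger readings also go too far:

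- *Observation time differs widely for all adverse events.* It differs by 28 days among the patients the SAP describes. A one-dose patient recorded only to day 91 is possible under the protocol, but SAP section 3.1 places no such patient in the analysed set.
- *Dropping tremelimumab cuts recording to day 91.* The run-in rule does allow "administering full doses of durvalumab but discontinuing tremelimumab after the first dose". But this case needs the rule to be triggered, and needs the last combination dose to mean the last co-administration rather than the last dose of the regimen.
- *Table 198 merges everything into one rate.* It has separate rows. The extension reaches only those that count related SAEs: SAE, SAE related, and the AE rows that include them.

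It can also be said that discontinuing might cover completion. Section 8.2.5 names completion and discontinuation separately, and SAP Table 39 separates completing the protocol treatment from stopping for toxicity, so that reading fits poorly. The wording still leaves some doubt.

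Finally, the trial has one arm and no formal safety test, so no comparison is biased. At n = 32 the 95% half-width around 10% is about 1.96 × √(0.1 × 0.9/32) = 10 points, larger than the effects illustrated. That limits the importance of the point but does not justify an avoidable difference in capture.

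**Conclusion.** The point holds for related SAEs. Section 10.3.1 sets an extended capture rule for early stoppers that its own reasoning would give to completers as well. Without progression the resulting period is about 5 times as long for the last patient enrolled and about 9 times for the first. The protocol sections and schedules also disagree on when safety capture ends, and Table 198 does not settle the matter with an onset window.

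The ratios rest on the planned dose days, on reading discontinuation as distinct from completion, and on no progression before closure. The 0.7 to 8.6 point effect is an illustration under assumed hazards and assumed numbers of early stoppers, and is not an estimate for this trial. For adverse events in general, the 28-day difference is minor. The primary efficacy analysis is not touched. This should be corrected because the unequal rule is written into the protocol and is easy to remove.

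**What to change.** 1. Reconcile sections 8.1.4, 8.1.5, 10.3.1, 10.3.9, 10.3.9.1 and 11.2.1 and both schedules to one AE/SAE recording window with one anchor date for all patients, and state whether radiotherapy counts towards that anchor. For a completer the choice hardly matters, since the last dose is on day 57 and the last fraction on about day 58.
2. After that window, apply late related-SAE capture in the same way to completers and early stoppers, at the follow-up visits already scheduled.
3. Restrict SAP Tables 198 to 208 to events with onset in the common window, state the window in each title or footnote, and list later related SAEs separately.

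AE start dates are already collected (section 10.3), so the third step needs no new data item. The cost is protocol and SAP wording, a few more late SAE reports from completers, and minor extra programming.
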